Except when explaining the trial details to the patient, this protocol will not be disclosed to any third party without the written consent of the trial coordinating committee and the investigational drug provider. Furthermore, the protocol cannot be used for any purpose other than the present trial.

Protocol Number:EPOC1603 Version number: Ver.1.7, Prepared: Apr, 09, 2020

Revision history:

Investigator-initiated trial protocol ver. 1.0, prepared: Sept, 12, 2017 Investigator-initiated trial protocol ver. 1.1, prepared: Jan, 22, 2018 Investigator-initiated trial protocol ver. 1.2, prepared: Febr, 2, 2018 Investigator-initiated trial protocol ver. 1.3, prepared: Aug, 20, 2018 Investigator-initiated trial protocol ver. 1.4, prepared: Feb, 25, 2019 Investigator-initiated trial protocol ver. 1.5, prepared: May, 8, 2019 Investigator-initiated trial protocol ver. 1.6, prepared: Aug, 19, 2019 Investigator-initiated trial protocol ver. 1.7, Prepared: Apr, 09, 2020

1. Summary

| Phase | Phase I |
|--------------|--|
| Subjects | Patients with unresectable recurrent solid tumors who are refractory or intolerant to |
| | standard chemotherapy |
| Objectives | Primary objective |
| | To examine the safety and tolerability of repeated dosing of regorafenib and nivolumab |
| | in patients with unresectable recurrent solid tumors who are refractory or intolerant to |
| | standard chemotherapy, and to investigate the maximum tolerated dose (MTD) and |
| | recommended dose (RD) of the drug when used in combination therapy. |
| | Dose-escalation cohort |
| | The safety of regorafenib and nivolumab combination therapy will be evaluated in |
| | patients with unresectable recurrent solid tumors who are refractory or intolerant to |
| | standard chemotherapy in order to determine the MTD and RD of regorafenib |
| | according to dose-limiting toxicity (DLT) when used in combination therapy. |
| | Expansion cohort |
| | An exploratory evaluation of the efficacy and safety of the combined treatment using |
| | the RD found in the dose-escalation cohort will be performed. |
| | Secondary objective |
| | • Safety |
| | - The incidences and types of adverse events that occur during treatment will be |
| | evaluated according to the National Cancer Institute (NCI) Common Terminology |
| | Criteria for Adverse Events (CTCAE) version 4.03. |
| | • Efficacy |
| | - Objective response rate (ORR) according to Response Evaluation Criteria in Solid |
| | Tumours (RECIST) version. 1.1, and immune-related (ir) RECIST |
| | - Progression-free survival (PFS) |
| | - Overall survival (OS) |
| | - Disease control rate (DCR) |
| | Exploratory items (performed as accompanying research in the present trial): |
| | Tests of various biomarkers |
| Trial design | The present trial is a phase I clinical trial intended to evaluate the safety of regorafenib |

| | and nivolumab combination therapy in patients with unresectable recurrent solid |
|-------------|---|
| | tumors who are refractory or intolerant to standard chemotherapy. |
| Trial study | Inclusion criteria |
| population | 1. Patients who provided written informed consent to be subjects in this trial |
| | 2. Patients at least 20 years of age on the day of providing consent |
| | 3. Dose-escalation cohort: Patients with histologically or cytologically confirmed |
| | advanced or metastatic solid tumors. |
| | Expansion cohort: Patients with histologically or cytologically confirmed |
| | advanced or metastatic solid tumors (gastric, colorectal, or hepatocellular cancer). |
| | 4. Patients with an Eastern Cooperative Oncology Group (ECOG) performance |
| | status (PS) of 0 or 1 |
| | 5. Patients capable of taking oral medication |
| | 6. Patients with evaluable or measurable lesions as per RECIST version 1.1 |
| | 7. Patients with adequate organ function at the time of enrollment as defined below: |
| | [Acceptable 7 days examination before the same day of the registration date] |
| | • Neutrophil count ≥ 1500 mm ³ |
| | • Platelet count $\geq 10.0 \times 10^4$ /mm ³ |
| | • Hemoglobin (Hb) \geq 9 g/dL, |
| | - aspartate transaminase (AST), alanine transaminase (ALT) $\leq 100 \text{ U/L}$ ($\leq 100 \text{ U/L}$ in |
| | patients with Hepatocelular carcinoma, ≤ 250 U/L in patients with liver metastasis) |
| | • Total bilirubin \leq 1.5mg/dLtimes the upper limit of normal |
| | • Creatinine ≤1.5mg /dL |
| | • Urinary protein: It satisfies one of the following (if any of the inspection criteria are |
| | satisfied, other examination may not be carried out) |
| | (i) urinary protein (test paper method) is 2+ or less |
| | (ii) UPC (Urine Protein Creatinine) ratio <3.5 |
| | (iii) 24-hour urine protein was measured, urinary protein $\leq 3500 \text{ mg}$ |
| | • PT-INR: ≤ 1.5 (≤ 3.0 in case of anticoagulant administration) |
| | * It is Child A in the case of Expansion cohort's hepatocellular carcinoma |
| | 8. For women who are likely to become pregnant (including those without |
| | menstruation due to medical reasons such as chemical menopause) Note 1, we |
| | agreed to double contraceptive Note 2 for at least 5 months after the final |
| l | administration of the investigational product from consent acquisition patient. |
| l | Also, patients who agreed not to breast feeding for at least 5 months after the final |
| | investigational drug administration after acquiring consent. |
| | |

For men, patients agreeing to double contraceptive for at least 7 months after the final investigational drug administration from the time of starting investigational drug administration.

Note 1): A woman who is likely to become pregnant is a woman who has experienced menarche and is not undergoing sterilization surgery (such as hysterectomy, bilateral salpingo ligation or bilateral oophorectomy), a woman without menopause Everything is included. The definition after menopause shall be amenorrhea continuously for 12 months or more even though there is no noteworthy reason. Women who are using oral contraceptives or mechanical contraceptive methods (such as intrauterine contraceptive devices or barrier methods) are considered to be pregnant.

Note 2): With regard to contraception, it is necessary to use two of the vasectomy or condom of a male patient or male male, the uterine tube ligation of a female patient or the other woman, a contraceptive pessary, an intrauterine contraceptive device or an oral contraceptive I need to agree to heavy contraception.

Exclusion criteria

- Patients who have undergone systemic chemotherapy, radiotherapy, surgery, hormone therapy, or immunotherapy <2 weeks before enrollment. Immune checkpoint blockade as pretreatment is permitted.
- 2. Patients with a history of taking regorafenib.
- Patients with hypertension that is difficult to control (systolic blood pressure ≥160 mmHg and diastolic blood pressure ≥90 mmHg) despite treatment with several hypotensive agents
- 4. Patients with acute coronary syndrome (including myocardial infarction and unstable angina), and with a history of coronary angioplasty or stent placement performed within 6 months before enrollment
- 5. Patients with a large amount of pleural effusion or ascites requiring drainage.
- 6. Patients with a \geq grade 3 active infection according to NCI-CTCAE version 4.03
- 7. Patients with symptomatic brain metastasis
- 8. Patients with partial or complete gastrointestinal obstruction
- 9. Patients with interstitial lung disease with symptoms or signs of activity
- 10. Patients who test positive for either anti-HIV-1 antibodies, anti-HIV-2 antibodies, hepatitis B surface antigen (HBsAg), or anti-hepatitis C virus (HCV) antibodies*
 *Patients who test positive for either anti-HBs or anti-HBc antibodies, and those who have HBV-DNA measurements greater than the detection sensitivity will

| | also be excluded. |
|----------------|---|
| | (However, patients with hepatocellular carcinoma in the expansion cohort will not |
| | be excluded even if they test positive for HBsAg and anti-HCV antibodies.) |
| | 11. Patients with concurrent autoimmune disease, or a history of chronic or recurrent |
| | autoimmune disease |
| | 12. Patients who require systemic corticosteroids (excluding temporary usage for |
| | tests, prophylactic administration for allergic reactions, or to alleviate swelling |
| | associated with radiotherapy) or immunosuppressants, or who have received such |
| | a therapy <14 days before enrollment in the present study |
| | 13. Patients with a history or findings of ≥grade III congestive heart failure according |
| | to the New York Heart Association functional classification |
| | 14. Patients with a seizure disorder who require pharmacotherapy |
| | 15. Patients who had grade 3 or higher bleeding during 4 weeks before enrollment. |
| | 16. Patients undergoing major surgery (thoracotomy or laparotomy, etc.), laparotomy |
| | biopsy, trauma within 28 days before registration. The same day of the week |
| | before 4 weeks can be registered |
| | (However, in case of an artificial anastomosis without intestinal resection, it shall |
| | be within 14 days before registration). |
| | 17. Non-healing wound, non-healing ulcer, or non-healing bone fracture. |
| | 18. Patients with a history of hypersensitivity to any of the study drugs, similar drugs, |
| | or excipients. |
| | 19. Pregnant women, lactating women or possibly pregnant women |
| Trial | The investigational drug will be repeatedly administered until the criteria for |
| participation | discontinuation are met. |
| period | In the event that the treatment is discontinued for reasons other than an exacerbation of |
| _ | the underlying disease via imaging (e.g., unacceptable side effects), tumor evaluation |
| | follow-up will continue until either an exacerbation of the underlying disease is |
| | observed via imaging or a new anticancer treatment is initiated, whichever happens |
| | first. |
| Sample size | Dose-escalation cohort: A total of 3–6 patients per level, for a total of 9–18 patients |
| | Expansion cohort: Approximately 30 patients in total |
| Administration | Dose-escalation cohort |
| method | One course will last 28 days*, and tolerability will be verified for the following |
| | dosages. |
| | Level 1 |
| | Regorafenib: Oral administration at a dose of 80 mg/day for 21 consecutive days, with |

| | a 1-week washout period. |
|-------------|--|
| | Nivolumab: Given once every 2 weeks at a dose of 3.0 mg/kg. |
| | When it is deemed that there are no safety issues associated with the above dosages, |
| | tolerability will be verified for the following level-2 dosages. |
| | Level 2 |
| | Regorafenib: Oral administration at a dose of 120 mg /day for 21 consecutive days, |
| | with a 1-week washout period. |
| | Nivolumab: Given once every 2 weeks at a dose of 3.0 mg/kg. |
| | Level 3 |
| | Regorafenib: Oral administration at a dose of 160 mg /day for 21 consecutive days, |
| | with a 1-week washout period. |
| | Nivolumab: Given once every 2 weeks at a dose of 3.0 mg/kg. |
| | When tolerability has been confirmed for the level-3 dosages, the above dosages will |
| | be the recommended dosages. |
| | |
| | The administered dose will increase using a $3 + 3$ design in accordance with the DLT. |
| | Three or more patients will be enrolled at each level. In the event that DLT is not |
| | observed during the initial course in the first three patients, these patients will move |
| | onto the next level. In the event that DLT is observed in one of the first three patients, |
| | an additional three patients will be added to the level in question. When all three |
| | additional patients have completed the first course without presenting with any DLT, |
| | these patients will move onto the next level. If DLT is observed in one of the three |
| | additional patients, an additional three patients will be added to the level below to |
| | determine the MTD. |
| | |
| | Expansion cohort: The trial will be conducted using the estimated RD found in the |
| | dose-escalation cohort. |
| Safety | Evaluations will be performed using CTCAE version 4.03. |
| evaluation: | |
| Efficacy | The antitumor effect will be evaluated in accordance with irRECIST and RECIST |
| evaluation: | version 1.1. The tumor evaluation will be performed as follows: |
| | • Image evaluation: computed tomography (CT) or magnetic resonance imaging (MRI) |
| | • Image evaluation schedule: evaluations will be performed at baseline as well as at 6, |
| | 12, 18, and 24 weeks (thereafter every 9 weeks until week 42 and subsequently every |
| | 12 weeks after week 42). |
| | |

| | PFS and OS will be evaluated in all subjects. |
|-----------------|--|
| TR | TR: A separate protocol will be prepared and implemented as ancillary research |
| Observation | Physical measurements, vital signs, PS, laboratory tests (i.e., blood and biochemistry), |
| and test items | urine analysis, clinical laboratory findings, tumor markers, as well as chest, abdominal |
| | and pelvic CT or MRI, etc. |
| Trial design | The present trial will comprise a dose-escalation cohort to simultaneously examine |
| | clinically RDs and tolerability of nivolumab and regorafenib combination therapy in |
| | patients with solid tumors, and an expansion cohort to examine the safety and efficacy |
| | of the clinically RDs in patients with multiple advanced solid tumors. |
| | In the dose-escalation cohort, three patients with solid tumors will be administered |
| | nivolumab at a dose of 3.0 mg/kg once every 2 weeks, and regorafenib at a dose of 80 |
| | mg (level 1), 120 mg (level 2) or 160 mg (level 3) for 21 consecutive days, with a |
| | 1-week washout period. As a general rule, one cycle will last 28 days (day 1-29). The |
| | DLT evaluation period will be 28 days. Furthermore, for each level, three additional |
| | subjects will be added depending on the occurrence of DLT. |
| | In the expansion cohort, approximately 30 patients with solid tumors will be |
| | administered the clinically RD of regorafenib found in the dose evaluation cohort. |
| Scheduled trial | Planned enrollment period: January 2018 to October 2018 (10 months)Planned |
| period | follow-up period: Two years from the last day of patient enrollment |
| | Overall trial period (including the procedures for trial completion): 2 years and 6 |
| | months after the last day of patient enrollment |
| | When the administration of all subjects would be completed during the observation |
| | period, the observation period of this study will be also terminated at the end of the |
| | observation period of the last administered patient. |

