4 INCLUSION AND EXCLUSION CRITERIA

4.1 Inclusion criteria

- 1. Patients who provided written informed consent to be subjects in this trial
- 2. Patients at least 20 years of age on the day of providing consent
- Dose-escalation cohort: Patients with histologically or cytologically confirmed advanced or metastatic solid tumors.

Expansion cohort: Patients with histologically or cytologically confirmed advanced or metastatic solid tumors (gastric, colorectal, or hepatocellular cancer).

- 4. Patients with an Eastern Cooperative Oncology Group (ECOG) performance status (PS) of 0 or 1
- 5. Patients capable of taking oral medication
- 6. Patients with evaluable or measurable lesions as per RECIST version 1.1
- Patients with adequate organ function at the time of enrollment as defined below: [Acceptable 7 days examination before the same day of the registration date]
 - Neutrophil count $\geq 1500/\text{mm}^3$
 - Platelet count $\geq 10.0 \times 10^4$ /mm³ (transfusion >2 weeks before testing permitted)

• aspartate transaminase (AST), alanine transaminase (ALT) $\leq 100 \text{ U/L2.5-times}$ the upper limit of normal (200U/L I patients with hepatocellular cancer ,or $\leq 250 \text{U/L}$ in patients with liver metastasis)

- Total bilirubin ≤ 1.5 -mg/dL
- Creatinine ≤ 1.5 -times the upper limit of normal
- Urinary protein: It satisfies one of the following (if any of the inspection criteria are satisfied, other examination may not be carried out)
 - (i) urinary protein (test paper method) is 2+ or less
 - (ii) UPC (Urine Protein Creatinine) ratio <3.5
 - (iii) 24-hour urine protein was measured, urinary protein $\leq 3500 \text{ mg}$
 - PT-INR: $\leq 1.5 \ (\leq 3.0 \text{ in case of anticoagulant administration})$
 - * It is Child A in the case of Expansion cohort's hepatocellular carcinoma
- 8. For women who are likely to become pregnant (including those without menstruation due to medical reasons such as chemical menopause) Note 1, we agreed to double contraceptive Note 2 for at least 5 months after the final administration of the investigational product from consent acquisition patient. Also, patients who agreed not to breast feeding for at least 5 months after the final investigational drug administration after acquiring consent.

For men, patients agreeing to double contraceptive for at least 7 months after the final investigational drug administration from the time of starting investigational drug administration.

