6.1.3 Definition of DLT

As a general rule, DLT includes the observation of any of the side effects listed below during the DLT evaluation period and will ultimately be determined upon deliberation between the sponsor and the principal investigator of the trial. Furthermore, the opinion of the Data and Safety Monitoring Committee can be sought as required (refer to attachment 1: trial protocol [supplement]).

• Hematotoxicity:

–Persistent grade 4 neutropenia lasting \geq 7 days;

-When a neutrophil count of <1000/mm³ and fever of $\ge 38.0^{\circ}$ C is observed for >2 days;

-Grader 4 thrombopenia or thrombopenia associated with a hemorrhage requiring platelet transfusion.

- Grade 3 thrombocytopenia with bleeding.

• Non-hematotoxicity:

 \geq Grade 3 non-hematotoxicities. However, any of the following non-hematotoxicities will be deemed DLT when it is judged by the principal investigator or subinvestigator that treatment cannot be continued even with supportive therapy.

- \Rightarrow 2Grade 3 diarrhea, nausea, vomiting, and loss of appetite for \geq 5 consecutive days;
- \Rightarrow 2Grade 3 electrolyte imbalance for 27 consecutive days;
- \Rightarrow \geq Grade 3 dermal toxicity for \geq 7 consecutive days;
- ♦ Grade 3 or more immune related adverse event that lasts more than 8 days even after steroid therapy is applied.

• General:

When 70% of the planned regorafenib dose cannot be administered, and/or when one dose of nivolumab cannot be administered because of toxicity during the DLT evaluation period

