6.3.1.3 Dose adjustment for elevated AST, ALT, and T-Bil levels

When an increase in AST, ALT, and/or T-Bil levels is observed during regorafenib treatment for which a causal relationship cannot be ruled out, the dose will be adjusted with reference to "Table 5: Dose adjustments for elevated AST, ALT, and T-Bil levels."

It is recommended to conduct liver function tests at least once a week until the liver function test results return to within the normal range or return to the grade at the time of enrollment.

| NC | I CTCAE Grade | Expression times | Dose adjustment |
|---------|---|--------------------------|--|
| Grade 2 | T-Bil exceeds 1.5 times the normal value upper limit and 3 times or less If AST or ALT exceeds 3 times the normal value upper limit and is 5 times or less | Regardless of the number | Continue administration and continue at least once a week for at least 4 weeks until T-Bil is less than 1.5 times the upper limit of normal value, AST or ALT is less than 3 times upper limit of normal value or recovered to Grade before administration, AST, ALT And T - Bil measurement should be carried out. |
| Grade 3 | T-Bil exceeds 3 times the normal value upper limit and is 10 times or less If AST or ALT exceeds 5 times the normal value upper limit and is 20 times or less | First time | Regorafenib is withdrawn until T-Bil is less than 1.5 times the upper limit of normal value and AST or ALT is recovered to less than 3 times normal value upper limit or below registered Grade. When dosing is resumed, it is recommended to reduce the same amount or 1 level and measure AST, ALT and T-Bil once a week for a minimum of 4 weeks. |
| | | Second time | Discontinue administration. |
| Grade 4 | T-Bil exceeds the normal value upper limit by 10 times AST or ALT is over 20 times the normal value upper limit | Regardless of the number | Discontinue administration. |

Table 5: Dose adjustment for elevated AST, ALT, and T-Bil levels

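### The 250 U/L AST/ALT entry limit for liver metastasis lies in grade 3 for any ULN below 50, and the DLT definition has no baseline clause for patients who enter there

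*Combined protocol and SAP*

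**What the plan says.** **Entry.** Summary criterion 7 admits AST/ALT "≤ 250 U/L in patients with liver metastasis", and section 4.1 item 7 gives the same limit. The dose-escalation cohort takes any advanced or metastatic solid tumor, so these patients can be DLT-evaluable. Neither section states a ULN. The only link is a garbled line in 4.1 that prints 100 U/L next to 2.5 times "the upper limit of normal (200U/L I patients with hepatocellular cancer".

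**Grading.** Table 5 in 6.3.1.3 gives the grade 3 range: "If AST or ALT exceeds 5 times the normal value upper limit and is 20 times or less". Grade 4 lies above 20 x ULN.

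**DLT.** Section 6.1.3 counts "Grade 3 non-hematotoxicities" (printed after a ≥ sign). Conditional items follow for gastrointestinal events, electrolytes, skin and persistent immune-related events. AST/ALT is not named, and neither 6.1.3 nor 6.1.4 mentions baseline. The list applies as a general rule, and a DLT "will ultimately be determined upon deliberation between the sponsor and the principal investigator of the trial".

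**Baseline wording elsewhere.** Section 10.1.1 includes abnormal laboratory changes among adverse events and says that pre-treatment findings count only if the grade worsens. That second sentence is worded for symptoms. Footnote a to Table 6 (6.3.2) has a nivolumab rule for liver metastasis and HCC: 50% above baseline for at least 1 week.

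**The concern.** A patient may enter escalation at an enzyme level that the protocol elsewhere treats as grade 3 toxicity. At that level Table 5 stops the drug ("Regorafenib is withdrawn until T-Bil is less than 1.5 times the upper limit of normal value", with a matching AST/ALT condition), Table 6 terminates nivolumab subject to footnote a, and 6.1.3 sets the DLT line. For such a patient the grade cannot do its usual job of separating a stable value from a large treatment-related rise.

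This matters because the MTD rests on very few calls. Under 6.1.2, no DLT in 3 patients escalates, 1 in 3 adds three patients, 1 in 6 passes and 2 in 6 fails the level. One call that depends on which section is taken to govern can change the decision.

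**Working it through.** The plan gives no figure to reproduce, so the check is threshold arithmetic plus an illustration.

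**1. Where the entry limit falls.** Inputs: limit 250 U/L (Summary and 4.1); grade 3 above 5 x ULN and grade 4 above 20 x ULN (Table 5).

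- Break-even ULN: 250 / 5 = 50 U/L. Below 50, the limit is in grade 3; at exactly 50 it is 5.0 x ULN and still grade 2.
- ULN implied by 4.1, if its two figures are equivalent: 100 / 2.5 = 40 U/L. This is an assumption.

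| ULN (U/L) | 250 as multiple of ULN | Grade 3 starts above | Grade 4 starts above |
|---|---|---|---|
| 30 | 8.33 | 150 | 600 |
| 35 | 7.14 | 175 | 700 |
| 40 | 6.25 | 200 | 800 |
| 45 | 5.56 | 225 | 900 |
| 50 | 5.00 (grade 2) | 250 | 1000 |

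**2. What the grade says for an entrant at 201-250 U/L (ULN 40).**

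- *If the grade-worsening rule in 10.1.1 governs laboratory values:* the next change is grade 4, above 20 x 40 = 800 U/L. That is a rise of 800 / 250 = 3.2-fold to 800 / 201 = 3.98-fold. A patient going from 230 to 780 U/L (780 / 230 = 3.39-fold) shows no grade change.
- *If it does not govern:* any rise attributed to the drug is a grade 3 side effect. From 230 to 240 U/L (240 / 230 = 1.04, a 4% rise) meets the line.

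**3. What else can make the call.** The dosing criterion in 6.1.3 ("When 70% of the planned regorafenib dose cannot be administered", or one nivolumab dose missed for toxicity) can act where the grade does not. If Table 5 withdrawal costs 7 of 21 days, 14 / 21 = 66.7% is given, below 70%; 6 lost days leave 15 / 21 = 71.4%. For nivolumab, the grade 3-4 row of Table 6 terminates the drug and points to footnote a, but the footnote names only grade 2. Otherwise the call rests on deliberation.

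**4. Possible effect on a level (illustration only).** With DLT rate p and q = 1 - p, a level passes with probability q³ + 3pq² x q³.

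- *Spurious calls:* if each patient has an extra chance m of a spurious AST/ALT DLT, replace p by 1 - (1 - p)(1 - m).

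| True p | m = 0 | m = 1% | m = 2% | m = 5% |
|---|---|---|---|---|
| 10% | 90.6% | 89.1% | 87.5% | 82.4% |
| 20% | 70.9% | 69.1% | 67.4% | 62.2% |

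- *Missed calls:* as an extreme bound, suppose one of the first three patients could register no DLT of any kind. Passing is then q² + 2pq x q³, which is 94.1% instead of 90.6% at p = 10%, and 80.4% instead of 70.9% at p = 20%. Masking liver enzymes alone would do less.

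The values of m and p are assumptions. The documents do not say how many patients enter above 5 x ULN.

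**The case against.** The strongest defence is that the protocol has enough rules outside the DLT list. Section 10.1.1 asks for a change, and for pre-existing findings a worsening of grade. DLTs are side effects, and 10.1.4 answers no on causality where there is a clear alternative explanation, for which liver metastasis with a raised entry value is an obvious candidate. Section 10.1.2 filters laboratory events through the physician. Table 5 applies only to an increase during treatment for which causality is not ruled out. Section 6.1.3 has its own condition for immune-related hepatitis ("Grade 3 or more immune related adverse event that lasts more than 8 days even after steroid therapy is applied"), and ends in deliberation.

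Most of this stands, and it rules out two stronger readings:

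- A reader might infer that a stable grade 3 entry value becomes a DLT automatically. The documents do not support this: an unchanged value is neither a change nor a side effect.
- A reader might infer that 6.1.3 judges non-hematological toxicity by grade alone, or that a rise from 190 to 205 U/L shows a special flaw. The rule also has duration, judgement and deliberation conditions. Crossing a line on a small rise from just below it is a property of any grade cut-off; it would remain at ULN 50, where 250 U/L is no longer grade 3.

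What the defence does not remove is the choice in step 2. Applying 10.1.1 protects the stable patient by making the grade insensitive up to 800 U/L. Not applying it restores sensitivity at the price of counting trivial drug-attributed rises. None of the softening rules states a baseline comparison for the DLT call.

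**Conclusion.** The point holds as a minor design weakness. The entry limit reaches grade 3 for any ULN below 50, and for patients entering there the DLT grade criterion is either insensitive until grade 4 or triggered by a small drug-attributed rise, depending on whether 10.1.1 applies to laboratory values. The call then falls to the dosing criterion or to case-by-case deliberation.

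The 201-250 and 800 U/L figures assume a ULN of 40, inferred from a garbled line; over ULN 30-45 grade 3 starts above 150-225 U/L. The effect on the MTD is small unless such patients are common. The arithmetic is firm, but the practical size is unknown.

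**What to change.** For the dose-escalation cohort, cap AST/ALT at entry for patients with liver metastasis at 5 x ULN. At ULN 40 this is 200 U/L, the figure that 4.1 already gives for hepatocellular cancer (the Summary gives 100 U/L for that group). Every DLT-evaluable patient would then enter below grade 3; if the local ULN is below 200 / 5 = 40, the hepatocellular limit in 4.1 needs the same cap. State the ULN, or express the limits as multiples of it.

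The cost is a wording change and the loss of patients entering above 5 x ULN, probably few but not stated. If escalation is already complete, list baseline AST/ALT beside each hepatic DLT decision instead.

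Carrying the footnote a threshold (50% above baseline for at least 1 week) into 6.1.3 is tempting but not advised. It would drop large short-lived rises: at ULN 40, 121 to 790 U/L for six days is a grade 3 rise on the current DLT line and would cease to count. Nor could it be confirmed for a rise first seen on day 22, because one week later is day 29, after the 28-day DLT window.
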